# 9.7.5 Procedure for Revising the Statistical Analysis Plan

If the SAP needs to be revised after the study starts, the sponsor will determine how the revision impacts the study and how the revision should be implemented. The details of the revision will be documented and described in the clinical study report.

Eisai Confidential Page 108 of 138

# 11 PROCEDURES AND INSTRUCTIONS (ADMINISTRATIVE PROCEDURES)

#### 11.1 Changes to the Protocol

Any change to the protocol requires a written protocol amendment or administrative change that must be approved by the sponsor before implementation. Amendments specifically affecting the safety of subjects, the scope of the investigation, or the scientific quality of the study require submission to health or regulatory authorities as well as additional approval by the applicable IRBs/IECs. These requirements should in no way prevent any immediate action from being taken by the investigator, or by the sponsor, in the interest of preserving the safety of all subjects included in the study. If the investigator determines that an immediate change to or deviation from the protocol is necessary for safety reasons to eliminate an immediate hazard to the subjects, the study medical monitor (or appropriate study team member) and the IRB/IEC for the site must be notified immediately. The sponsor must notify the health or regulatory authority as required per local regulations.

Protocol amendments that affect only administrative aspects of the study may not require submission to health or regulatory authority or the IRB/IEC, but the health or regulatory authority and IRB/IEC (or if regionally required, the head of the medical institution) should be kept informed of such changes as required by local regulations. In these cases, the sponsor may be required to send a letter to the IRB/IEC and the Competent Authorities (or, if regionally required, the head of the medical institution) detailing such changes.

#### 11.2 Adherence to the Protocol

The investigator will conduct the study in strict accordance with the protocol (refer to ICH E6, Section 4.5).

#### 11.3 Monitoring Procedures

The sponsor's/CRO's CRA will maintain contact with the investigator and designated staff by telephone, letter, or email between study visits. Monitoring visits to each site will be conducted by the assigned CRA as described in the monitoring plan. The investigator (or if regionally required, the head of the medical institution) will allow the CRA to inspect the clinical, laboratory, and pharmacy facilities to assure compliance with GCP and local regulatory requirements. The CRFs and subject's corresponding original medical records (source documents) are to be fully available for review by the sponsor's representatives at regular intervals. These reviews verify adherence to study protocol and data accuracy in accordance with local regulations. All records at the site are subject to inspection by the local auditing agency and to IRB/IEC review.

In accordance with ICH E6, Section 1.52, source documents include, but are not limited to, the following:

Eisai Confidential Page 111 of 138

- Clinic, office, or hospital charts
- Copies or transcribed health care provider notes that have been certified for accuracy after production
- Recorded data from automated instruments such as IxRS, x-rays, and other imaging reports (eg, sonograms, CT scans, magnetic resonance images, radioactive images, ECGs, rhythm strips, EEGs, polysomnographs, pulmonary function tests) regardless of how these images are stored, including microfiche and photographic negatives
- Pain, quality of life, or medical history questionnaires completed by subjects
- Records of telephone contacts
- Diaries or evaluation checklists
- Drug distribution and accountability logs maintained in pharmacies or by research personnel
- Laboratory results and other laboratory test outputs (eg, urine pregnancy test result documentation and urine dip-sticks)
- Correspondence regarding a study subject's treatment between physicians or memoranda sent to the IRBs/IECs
- CRF components (eg, questionnaires) that are completed directly by subjects and serve as their own source

#### 11.4 Recording of Data

A CRF is required and must be completed for each subject by qualified and authorized personnel. All data on the CRF must reflect the corresponding source document, except when a section of the CRF itself is used as the source document. Any correction to entries made on the CRF must be documented in a valid audit trail where the correction is dated, the individual making the correct is identified, the reason for the change is stated, and the original data are not obscured. Only data required by the protocol for the purposes of the study should be collected.

The investigator must sign each CRF. The investigator will report the CRFs to the sponsor and retain a copy of the CRFs.

#### 11.5 Identification of Source Data

All data to be recorded on the CRF must reflect the corresponding source documents.

#### 11.6 Retention of Records

The circumstances of completion or termination of the study notwithstanding, the investigator (or if regionally required, the head of the medical institution or the designated representative) is responsible for retaining all study documents, including but not limited to the protocol, copies of CRFs, the Investigator's Brochure, and regulatory agency registration documents (eg, Form FDA 1572, ICFs, and IRB/IEC correspondence). The site should plan

Eisai Confidential Page 112 of 138

to retain study documents, as directed by the sponsor, for at least 2 years after the last approval of a marketing application in an ICH region and until there are no pending or contemplated marketing applications in an ICH region or at least 3 years have elapsed since the formal discontinuation of clinical development of the investigational product.

It is requested that at the completion of the required retention period, or should the investigator retire or relocate, the investigator contact the sponsor, allowing the sponsor the option of permanently retaining the study records.

#### 11.7 Auditing Procedures and Inspection

In addition to routine monitoring procedures, the sponsor's Clinical Quality Assurance department conducts audits of clinical research activities in accordance with the sponsor's SOPs to evaluate compliance with the principles of ICH GCP and all applicable local regulations. If a government regulatory authority requests an inspection during the study or after its completion, the investigator must inform the sponsor immediately.

#### 11.8 Handling of Study Drug

All study drug will be supplied to the principal investigator (or a designated pharmacist) by the sponsor. Drug supplies must be kept in an appropriate secure area (eg, locked cabinet) and stored according to the conditions specified on the drug labels. The investigator (or a designated pharmacist) must maintain an accurate record of the shipment and dispensing of the study drug in a drug accountability ledger, a copy of which must be given to the sponsor at the end of the study. An accurate record of the date and amount of study drug dispensed to each subject must be available for inspection at any time. The CRA will visit the site and review these documents along with all other study conduct documents at appropriate intervals once study drug has been received by the site.

All drug supplies are to be used only for this study and not for any other purpose. The investigator (or site personnel) must not destroy any drug labels or any partly used or unused drug supply before approval to do so by the sponsor. At the conclusion of the study and as appropriate during the study, the investigator (or a designated pharmacist) will return all used and unused drug containers, drug labels, and a copy of the completed drug disposition form to the sponsor's CRA (or designated contractor) or, when approval is given by the sponsor, will destroy supplies and containers at the site.

#### 11.9 Publication of Results

All manuscripts, abstracts, or other modes of presentation arising from the results of the study must be reviewed and approved in writing by the sponsor in advance of submission pursuant to the terms and conditions set forth in the executed Clinical Trial Agreement between the sponsor/CRO and the institution/investigator. The review is aimed at protecting the sponsor's proprietary information existing either at the date of the commencement of the study or generated during the study.

Eisai Confidential Page 113 of 138

The detailed obligations regarding the publication of any data, material results, or other information generated or created in relation to the study shall be set out in the agreement between each investigator and the sponsor or CRO, as appropriate.

#### 11.10 Disclosure and Confidentiality

The contents of this protocol and any amendments and results obtained during the study should be kept confidential by the investigator, the investigator's staff, and the IRB/IEC and will not be disclosed in whole or in part to others, or used for any purpose other than reviewing or performing the study, without the written consent of the sponsor. No data collected as part of this study will be used in any written work, including publications, without the written consent of the sponsor. These obligations of confidentiality and non-use shall in no way diminish such obligations as set forth in either the Confidentiality Agreement or Clinical Trial Agreement executed between the sponsor/CRO and the institution/investigator.

All persons assisting in the performance of this study must be bound by the obligations of confidentiality and non-use set forth in either the Confidentiality Agreement or Clinical Trial Agreement executed between the institution/investigator and the sponsor/CRO.

#### 11.11 Discontinuation of Study

The sponsor reserves the right to discontinue the study for medical reasons or any other reason at any time. If a study is prematurely terminated or suspended, the sponsor will promptly inform the investigators/institutions and regulatory authorities of the termination or suspension and the reason(s) for the termination or suspension. The IRB/IEC will also be informed promptly and provided the reason(s) for the termination or suspension by the sponsor or by the investigator/institution, as specified by the applicable regulatory requirement(s).

The investigator reserves the right to discontinue the study should his/her judgment so dictate. If the investigator terminates or suspends a study without prior agreement of the sponsor, the investigator should inform the institution where applicable, and the investigator/institution should promptly inform the sponsor and the IRB/IEC and provide the sponsor and the IRB/IEC with a detailed written explanation of the termination or suspension. Study records must be retained as noted above.

#### 11.12 Subject Insurance and Indemnity

[figure not shown]
The sponsor will provide insurance for any subjects participating in the study in accordance with all applicable laws and regulations.

Eisai Confidential Page 114 of 138

#### 12 APPENDICES

Eisai Confidential Page 115 of 138

### Appendix 1 Identification and Documentation of Injectable and Biopsiable Lesions at Screening CT Scan

#: An injectable lesion can also be the biopsiable lesion if it has not been injected and there are other lesions available to be targeted for injecting with E7766.

Eisai Confidential Page 116 of 138

\*At Screening, the investigator can identify more than 1 lesion for injection. The sequence of lesion selection for injection should be agreed in advance by the investigator based on ease of accessibility and degree of risk (eg, bleeding) involved. In case additional lesions are required for injection, additional forms can be filled during the study as required.

Lesion Assessment for Injection and Biopsy		
Site Number:	Subject ID:	Date of Visit:
Visit ID:	Investigator:	
Sign	ature	Date (MM/DD/YYYY)
Print Name	e and Title	

Eisai Confidential Page 117 of 138

# Appendix Table 1: Target and Nontarget Lesion Definitions by LDi (Long Axis Diameter) and SDi (Short Axis Diameter) for Solid Tumors and Lymphoma

	Solid Tumor: Modified RECIST 1.1/iRECIST	Lymphoma: Lugano/LYRIC
Maximum number of target lesions	Up to 10 total Nodal/Extranodal Sites / max 5 per organ a	Up to 6 Nodal/Extranodal Sites
Target: Lymph Node	15 mm SDi	15 mm LDi
Target: non-Lymph Node	10 mm LDi	10 mm LDi
Non-Target: Lymph Node	10 mm SDi (pathological)	10 mm LDi (pathological)
Non-Target : non-Lymph Node	NA	NA

NOTE: An injectable lesion can also be selected as the lesion for biopsy if it has not been injected previously and there are other lesions available to be targeted for injecting with E7766.

iRECIST = modified RECIST 1.1 for immune-based therapeutics, LYRIC = LYmphoma Response to Immunomodulatory Therapy Criteria, RECIST 1.1 = Response Evaluation Criteria in Solid Tumours version 1.1.

Eisai Confidential Page 118 of 138

a: Lymph nodes are considered 1 organ system.

### Appendix 2 Description of the iRECIST Process for Assessment of Disease Progression

Assessment at Screening and Prior to modified RECIST 1.1 Progression

Until radiographic disease progression based on modified RECIST 1.1, there is no distinct iRECIST assessment.

Assessment and Decision at modified RECIST 1.1 Progression

For participants who show evidence of radiological PD by modified RECIST 1.1 as determined by the Investigator, the Investigator will decide whether to continue a participant on study treatment until repeat imaging is obtained (using iRECIST for participant management (Appendix Table 2). This decision by the Investigator should be based on the participant's overall clinical condition.

Clinical stability is defined as the following:

- Absence of symptoms and signs indicating clinically significant progression of disease
- No decline in ECOG performance status
- No requirements for intensified management, including increased analgesia, radiation, or other palliative care

Any participant deemed **clinically unstable** should be discontinued from study treatment, and is not required to have repeat tumor imaging for confirmation of PD by iRECIST.

If the Investigator decides to continue treatment, the participant may continue to receive study treatment and the tumor assessment should be repeated 4 to 8 weeks later to confirm PD by iRECIST, per Investigator assessment. Images should continue to be sent in to the central imaging vendor for potential retrospective independent imaging review (IIR) and exploratory analysis of tumor volume

Tumor flare may manifest as any factor causing radiographic progression per RECIST 1.1, including:

- Increase in the sum of diameters of target lesion(s) identified at baseline to ≥20% and >5 mm from nadir
  - Note: The iRECIST publication uses the terminology "sum of measurements," but "sum of diameters" will be used in this protocol, consistent with the original RECIST 1.1 terminology.
- Unequivocal progression of nontarget lesion(s) identified at baseline
- Development of new lesion(s)

Eisai Confidential Page 119 of 138

iRECIST defines new response categories, including iUPD (unconfirmed progressive disease per iRECIST) and iCPD (confirmed progressive disease per iRECIST). For purposes of iRECIST assessment, the first visit showing progression according to modified RECIST 1.1 will be assigned a visit (overall) response of iUPD, regardless of which factors caused the progression.

At this visit, target and nontarget lesions identified at baseline by modified RECIST 1.1 will be assessed as usual.

New lesions will be classified as measurable or nonmeasurable, using the same size thresholds and rules as for baseline lesion assessment in RECIST 1.1. From measurable new lesions, up to 5 lesions total (up to 2 per organ), may be selected as New Lesions – Target. The sum of diameters of these lesions will be calculated, and kept distinct from the sum of diameters for target lesions at baseline. All other new lesions will be followed qualitatively as New Lesions – Non-target.

Assessment at the Confirmatory Imaging

On the confirmatory imaging, the participant will be classified as progression confirmed (with an overall response of iCPD), or as showing persistent unconfirmed progression (with an overall response of iUPD), or as showing disease stability or response (iSD/iPR/iCR).

Confirmation of Progression

Progression is considered confirmed, and the overall response will be iCPD, if ANY of the following occurs:

- Any of the factors that were the basis for the iUPD at the previous visit show worsening
  - For target lesions, worsening is a further increase in the sum of diameters of
  - ≥5 mm, compared to any prior iUPD time point
  - For nontarget lesions, worsening is any significant growth in lesions overall, compared to a prior iUPD time point; this does not have to meet the "unequivocal" standard of RECIST 1.1
  - For new lesions, worsening is any of these:
    - An increase in the new lesion sum of diameters by ≥5 mm from a prior iUPD time point
    - Visible growth of new nontarget lesions
    - The appearance of additional new lesions
- Any new factor appears that would have triggered PD by modified RECIST 1.1

Persistent iUPD

Progression is considered not confirmed, and the overall response remains iUPD, if:

Eisai Confidential Page 120 of 138

- None of the progression-confirming factors identified above occurs AND
- The target lesion sum of diameters (initial target lesions) remains above the initial PD threshold (by modified RECIST 1.1)

Additional imaging for confirmation should be scheduled 4 to 8 weeks from the imaging on which the initial iUPD is seen. This may correspond to the next visit in the original visit schedule. The assessment of the subsequent confirmation imaging proceeds in an identical manner, with possible outcomes of iCPD, iUPD, and iSD/iPR/iCR.

#### Resolution of iUPD

Progression is considered not confirmed, and the overall response becomes iSD/iPR/iCR, if:

- None of the progression-confirming factors identified above occurs, AND
- The target lesion sum of diameters (initial target lesions) is not above the initial PD threshold

The response is classified as iSD or iPR (depending on the sum of diameters of the target lesions), or iCR if all lesions resolve.

In this case, the initial iUPD is considered to be pseudo-progression, and the level of suspicion for progression is "reset." This means that the next visit that shows radiographic progression, whenever it occurs, is again classified as iUPD by iRECIST, and the confirmation process is repeated before a response of iCPD can be assigned.

Management Following the Confirmatory Imaging

If repeat imaging does not confirm PD per iRECIST, as assessed by the Investigator, and the participant continues to be clinically stable, study treatment may continue and follow the regular imaging schedule. If PD is confirmed, participants will be discontinued from study treatment.

Detection of Progression at Visits After Pseudo-progression Resolves

After resolution of pseudo-progression (ie, achievement of iSD/iPR/iCR), iUPD is indicated by any of the following events:

- Target lesions
  - Sum of diameters reaches the PD threshold (≥20% and ≥5 mm increase from nadir) either for the first time, or after resolution of previous pseudo-progression. The nadir is always the smallest sum of diameters seen during the entire trial, either before or after an instance of pseudo-progression.
- Non-target lesions

Eisai Confidential Page 121 of 138

- If nontarget lesions have never shown unequivocal progression, their doing so for the first time results in iUPD.
- If nontarget lesions have shown previous unequivocal progression, and this progression has not resolved, iUPD results from any significant further growth of nontarget lesions, taken as a whole.
- New lesions
  - New lesions appear for the first time
  - Additional new lesions appear
  - Previously identified new target lesions show an increase of  $\geq 5$  mm in the new lesion sum of diameters, from the nadir value of that sum
  - Previously identified nontarget lesions show any significant growth

If any of the events above occur, the overall response for that visit is iUPD, and the iUPD evaluation process (see Assessment at the Confirmatory Imaging above) is repeated.

Progression must be confirmed before iCPD can occur.

The decision process is identical to the iUPD confirmation process for the initial PD, with one exception: if new lesions occurred at a prior instance of iUPD, and at the confirmatory imaging the burden of new lesions has increased from its smallest value (for new target lesions, the sum of diameters is ≥5 mm increased from its nadir), then iUPD cannot resolve to iSD or iPR. It will remain iUPD until either a decrease in the new lesion burden allows resolution to iSD or iPR, or until a confirmatory factor causes iCPD.

Additional details about iRECIST are provided in the iRECIST publication (Seymour, et al., 2017).

Eisai Confidential Page 122 of 138

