5.4.2.4 Progression-free Survival

In PFS analysis Subjects without disease progression or death will be censored at the time of the last tumor assessment. Subjects who started new anticancer therapies without documented progression of disease will be censored at the last adequate tumor assessment on or prior to the start of new anticancer therapies. Determination of the date of PFS event or censoring is summarized in [Table 3](#) below.

Table 3 PFS Event and Censoring Rules

No.	Situation	Date of Progression or Censoring	Outcome
1	No baseline or postbaseline adequate tumor assessments	Date of first dose	Censored
2	Progression documented between scheduled visits, on or prior to new anticancer therapy	Date of first qualified*** PD assessment	PFS Event
3	No progression at the time of data cutoff	Date of last adequate assessment on or prior to data cutoff	Censored
4	New anticancer therapy started	Date of last adequate assessment on or prior to the start of new anticancer therapy	Censored
5	Death before first PD assessment, on or prior to start of new anticancer therapy	Date of death	PFS Event
6	Death between adequate assessment*	Date of death	PFS Event
7	Death or progression after more than one missed visit/tumor assessment**	Date of last adequate assessment before missed tumor assessments	Censored

CR = complete response, ic = iRECIST-confirmed, iu = iRECIST-unconfirmed, PD = progressive disease, PR = partial response, SD = stable disease.

Note:

* Adequate tumor assessment is radiologic assessment of CR, PR, SD, non-CR/non-PD or PD as determined by investigators at regular interval as defined in the protocol. Any tumor assessments after new anticancer therapy will not be considered in the definition of PFS.

** More than one missed visit/adequate tumor assessment is defined as:

- having the duration between two consecutive tumor assessments or the duration between the last adequate tumor assessment and death/PD being longer than (>) 97 days (for solid tumors because the scans are scheduled every 6 weeks \pm 7 days for this study).

*** Qualified PD is defined as:

- For modified RECIST: the documented PD per modified RECIST CRF page;
- For iRECIST: in the order of 1) the documented iCPD per iRECIST CRF page, or 2) the iUPD that has not be reset by subsequent iCR/iPR/iSD

NOTE: iCPD has to be within 8 weeks of iUPD, but not earlier than 4 weeks (i.e. \geq 28 days) of iUPD.

1. If the subject had PD or death, the following sequence will be applied:

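### A first iUPD caused only by a new or non-target lesion cannot persist as iUPD: without a confirming factor it resets to iSD or iPR even if that lesion is unchanged

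*Protocol*

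**What the plan says.** Under Protocol Appendix 2, the first visit that meets progression by modified RECIST 1.1 "will be assigned a visit (overall) response of iUPD, regardless of which factors caused the progression". The cause may be target growth, unequivocal non-target progression or a new lesion.

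The confirmatory scan has three possible outcomes.

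- **Confirmed (iCPD)** if any listed factor occurs. For new lesions these are "An increase in the new lesion sum of diameters by ≥5 mm from a prior iUPD time point", "Visible growth of new nontarget lesions", or a further new lesion. Significant non-target growth, a further target increase of at least 5 mm, or any new progression trigger also confirms.
- **Persistent iUPD** if no confirming factor occurs and "The target lesion sum of diameters (initial target lesions) remains above the initial PD threshold (by modified RECIST 1.1".
- **Reset** if two conditions hold. The first is "None of the progression-confirming factors identified above occurs, AND"; the second is "The target lesion sum of diameters (initial target lesions) is not above the initial PD threshold". The visit becomes iSD or iPR according to the baseline target sum. Only iCR requires every lesion to have gone.

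For an iUPD that follows an earlier resolved pseudo-progression, Appendix 2 adds an exception. If new-lesion burden has risen from its smallest value (by at least 5 mm for new target lesions), the visit cannot resolve: "It will remain iUPD until either a decrease in the new lesion burden allows resolution to iSD or iPR".

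SAP Section 5.4.2.4, Table 3, note *** defines qualified progression under iRECIST as, in order, a documented iCPD or "the iUPD that has not be reset by subsequent iCR/iPR/iSD". SAP Sections 5.1.1 and 5.1.2 use qualified progression for DOR and PFS.

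**The concern.** Neither the persistence test nor the reset test looks at the finding that raised the iUPD, unless that finding was target growth. A subject whose new lesion is still present and unchanged is recorded as having had pseudo-progression. The protocol justifies treatment past first progression by a transient flare (Section 9.5.1.3.1), and a lesion that is still there does not obviously fit that description.

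The label carries into the analysis. The iSD or iPR feeds iRECIST DCR and ORR, and the reset removes the iUPD from PFS and DOR. The direction is towards more responders, more disease control and later progression. Readers may find this hard to detect: SAP Section 7 removes the tumor-assessment listings from the abbreviated report. The SAP's cross-reference to its best-overall-response rule does not resolve in the available text, so I could not check whether that rule corrects the label.

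**Working it through.** The plan gives no figure to reproduce, so the check applies the Appendix 2 rules literally.

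**Step 1. First iUPD caused only by a new lesion, baseline target sum not above the progression threshold.**

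| Finding at the confirmatory scan | Outcome |
|---|---|
| New Lesions – Target sum changes by −3, 0, +2, +4 or +4.9 mm | Reset to iSD or iPR |
| New Lesions – Target sum changes by +5 or +8 mm | iCPD |
| Visible growth of a new non-target lesion | iCPD |
| An additional new lesion | iCPD |
| Target sum now crosses the threshold | iCPD (new progression trigger) |

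Persistent iUPD never appears. It needs the target sum to remain above a threshold that it had not crossed. If the sum crosses later, that is itself a confirming factor. The same holds for a first iUPD from non-target progression alone: significant further growth confirms, and an unchanged finding resets.

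**Step 2. Stable new lesion (constructed example).** Target sum is 60 mm at baseline and 40 mm at weeks 6, 12 and 18. A new measurable lesion is 12 mm at all three scans.

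- Week 6: new lesion, so iUPD.
- Week 12: new-lesion change 12 − 12 = 0 mm, below 5; target sum not above threshold; reset. Target fall (60 − 40)/60 = 33%, which I assume is enough for partial response because Appendix 2 does not restate the cut-off. Result: iPR.
- Week 18: no re-trigger, so iPR again. Six weeks exceeds the four-week minimum, so the response is confirmed.

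This subject is an iRECIST responder with no iRECIST PFS event from that lesion. Under modified RECIST 1.1 the same subject progressed at week 6.

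**Step 3. Slowly growing new lesion (constructed example).** The new lesion is 12 mm at week 6 and grows 4 mm every 6 weeks, with a stable target sum.

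- Week 12: 16 mm, +4, reset.
- Week 18: 20 mm, +8 from nadir, iUPD again.
- Week 24: 24 mm. This is iCPD if measured against week 6 (+12). If measured only against week 18 (+4), it stays iUPD under the exception.

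Progression is delayed here, not lost, and the delay depends on the dating convention:

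- If PFS is dated at the first iUPD not reset, the event moves from week 6 to week 18: 12 weeks, or 84 days.
- If PFS is dated at iCPD, with growth measured from week 6, an iUPD held open at week 12 would be confirmed at week 18 (20 − 12 = 8 mm). With the reset, confirmation comes at week 24: 6 weeks, or 42 days, later.

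Note *** lists iCPD first but does not say which date applies when both exist.

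**Step 4. Weight of one subject.** One subject moves ORR or DCR by 100/n points: 100/35 = 2.9 and 100/40 = 2.5. Exact (Clopper-Pearson) 95% intervals:

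| n | 0 responders | 1 responder |
|---|---|---|
| 35 | 0% (0 to 10.0%) | 2.9% (0.1 to 14.9%) |
| 40 | 0% (0 to 8.8%) | 2.5% (0.1 to 13.2%) |

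SAP Section 7 says escalation ended early. If fewer subjects were treated, each one weighs more.

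**The case against.** The strongest defence is that the rule is deliberate. After a reset, Appendix 2 goes on tracking previously identified new lesions and unresolved non-target progression, so it expects lesions to remain, and it supplies re-triggers. Requiring shrinkage is a different design choice. That stands as far as intent goes. It does not explain why an unchanged lesion should earn iPR or drop out of PFS.

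The later-iUPD exception is also a weaker precedent than it looks. At the first confirmatory scan the new-lesion nadir is normally the iUPD value itself, so growth of 5 mm or more from nadir already confirms progression. Copying the exception to a first iUPD would change little for new target lesions. What carries over is its principle that resolution waits for a decrease in new-lesion burden.

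Modified RECIST 1.1 is reported in parallel with no reset, so readers see the progression there. This limits the harm but does not correct the iRECIST results.

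The fix has a price. Note *** counts an unreset iUPD as progression even if it is never confirmed. Holding the iUPD open for an unchanged new lesion therefore moves the iRECIST result towards the modified RECIST 1.1 result for these subjects. A derived call may also differ from the investigator's CRF entry, and the endpoint is investigator-assessed. Both points stand and should be stated openly.

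Impact is limited. SAP Sections 3.2.2 and 7 cancel the expansion part, where these endpoints were primary, and SAP Section 5.3.3 plans no comparisons.

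**Conclusion.** The point holds as a gap in the iRECIST derivation. A first iUPD from a new or non-target lesion alone can end only in confirmation or reset, and the reset ignores whether the cause is still present. Possible progressions may be misclassified (Step 2) or delayed (Step 3) in iRECIST ORR, DCR, DOR and PFS of the escalation part. One subject is worth 2.5 to 2.9 points of ORR or DCR at 35 to 40 subjects. This is worth correcting but does not threaten the study's safety objectives.

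A reader might infer more than the documents support:

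- *That reset follows whenever the target sum is below threshold.* It does not. The first condition excludes every confirming factor, and the allowance below 5 mm applies only to lesions followed as New Lesions – Target.
- *That true progressions are turned into responses.* Nothing in the documents shows that an unchanged new lesion is true progression, and continued growth re-triggers iUPD.
- *That a known share of progressions is affected, or that PFS shifts by a fixed time.* No frequency is given, and the shift depends on an unsettled dating rule.
- *That Appendix 2 departs from the cited iRECIST publication.* That cannot be checked here; the case rests on the plan's own text.

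**What to change.** Reconcile the persistence and resolution rules of Appendix 2 with its later-iUPD exception, for endpoint derivation only.

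1. In SAP Table 3, note ***, and in the iRECIST best-overall-response derivation, state that an iUPD caused by a new or non-target lesion is not treated as reset, and iSD or iPR is not credited, while that lesion persists without decrease.
2. State whether iRECIST PFS is dated at iCPD or at the original iUPD when both exist.
3. Report the number of resets in which the causal lesion persisted.

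Leave the treatment instructions in Appendix Table 2 as they are.

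The cost is some wording and a programmed check on lesion data already collected. The downsides are somewhat fewer iSD or iPR calls, earlier iRECIST PFS events, and a derived call that may differ from the investigator's CRF entry. Show both calls where they disagree.
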